### **Methods:**

Participants will be recruited through convenience sampling and will provide written informed consent. We will conduct surveys in three counties with a similar distribution of participants to gauge PT4A Protocol 1.4 23rd November, 2022

perspectives from various stakeholders in the model; this will include patients, peers, and clinical staff. Initial prototype diagrams will be shared with the group and presented from the perspective of each type of stakeholder to fully inform them of their role within the model. A structured questionnaire will be used to elicit constructive feedback from the group.

#### **Outcomes and Analysis:**

Statistical Analysis will include descriptive statistics of outcomes of interest including:

1) Satisfaction with the proposed intervention design, 2) perceived appropriateness, 3) fit within existing community and clinical infrastructures, 4) perceived positive or negative effects, 5) expressed interest or intention to participate, 6) perceived relevance to address adherence to medication, 7) barriers to implementation within existing community and clinical infrastructure, 8) ease of implementing this intervention. At the conclusion of this analysis, the design team will meet to review these outcomes and refine the intervention model as necessary to enhance acceptability.

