### **Subaim 2.1: Evaluate the intervention for acceptability and appropriateness**

After the PT4A model prototype is created we will evaluate how applicable and workable the core components of PT4A will be more so in terms of cost, complexity, usability, and value.

Participants (targeted number of 39 in total will be enrolled), this will include representatives of the end users of our product, which includes: hypertension patients (5 per site), clinicians (5 per site), pharmacy (1 per site) and peers (6 in total). Participants will be recruited through convenience sampling within the 3 counties where we will conduct the study. Participants will be reimbursed for time and travel through PT4A funds during those sessions.

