**Medication packaging**

The medication was properly sealed during the delivery

- All the time
- A lot of the time
- Some of the time
- None of the time

The medication was properly labeled and the dosage indicated

- All the time
- A lot of the time
- Some of the time
- None of the time

The medication was properly labeled and the dosage indicated

- All the time
- A lot of the time
- Some of the time
- None of the time

The peer was able to give you instructions for medication use

- All the time

 A lot of the time  Some of the time  None of the time
The medication brand changes were clearly communicated  All the time  A lot of the time  Some of the time  None of the time
The medication payments reflected the amount of medication received  All the time  A lot of the time  Some of the time  None of the time
Total Scores _____

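### Three of the eight Sub-Aim 2.1 outcomes (perceived effects, barriers, ease of implementing) have no item on any of the three Sub-Aim 2.1 forms printed in Appendix B

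*Combined protocol and SAP*

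**What the plan says.** Appendix A, Subaim 2.1, Outcomes and Analysis, sets out the analysis: "Statistical Analysis will include descriptive statistics of outcomes of interest including" eight named outcomes. The first six concern satisfaction with the design, appropriateness, fit with local infrastructure, expected good or bad effects, interest in taking part, and relevance to adherence. The list then closes with two on implementation: "7) barriers to implementation within existing community and clinical infrastructure, 8) ease of implementing this intervention".

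The Methods paragraph just above names the source: "A structured questionnaire will be used to elicit constructive feedback from the group". The introduction to Subaim 2.1 says the prototype is to be judged "more so in terms of cost, complexity, usability, and value". The results have a stated use: "the design team will meet to review these outcomes and refine the intervention model as necessary to enhance acceptability". That happens at Design Team Meeting #5, which Appendix A places before the pilot.

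Appendix B prints three Sub-Aim 2.1 forms, for patients, the health care team and peers. Each has background questions, four Acceptability of Intervention Measure (AIM) items and four Intervention Appropriateness Measure (IAM) items.

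Appendix B also holds the pilot (Sub-Aim 2.2) patient questionnaires. In the Medication packaging block of the delivery process and completeness form, the item "The medication was properly labeled and the dosage indicated" is printed twice in succession, each time with its own response list. A single total line follows at the end of the form.

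**The concern.** A descriptive analysis can report only what was asked. If an outcome is on the analysis list but on none of the forms meant to collect it, the result will be missing, or someone will have to infer it afterwards from items that do not measure it.

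The gap falls on outcomes that would tell a design team what to change. Acceptability and appropriateness ratings show whether respondents like the model. They do not show what obstructs it, how hard it would be to run, or what harm or benefit people expect. Meeting #5 is also meant to sort issues raised in the surveys into themes, and closed agreement ratings raise few issues to sort.

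The repeated item on the pilot form is a separate and smaller matter. If the form is totalled as printed, labelling counts twice.

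**Working it through.** **Inputs.** The eight outcomes and the 39 participants come from Appendix A, Subaim 2.1. The items come from the three Sub-Aim 2.1 forms and the pilot patient forms in Appendix B.

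**Step 1: the plan's own figure.** Patients 5 × 3, clinicians 5 × 3, pharmacy 1 × 3 and peers 6 give 15 + 15 + 3 + 6 = 39. This matches the stated target and is not in dispute.

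**Step 2: outcomes against items.** The AIM items cover meeting needs, appeal, liking and wish to enrol (self or patients). The IAM items cover fitting, suitable, applicable and good match.

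| Outcome | Nearest item on the Sub-Aim 2.1 forms | Covered? |
|---|---|---|
| 1 Satisfaction | AIM: needs, appeal, liking | Yes |
| 2 Appropriateness | All four IAM items | Yes |
| 3 Fit with infrastructure | IAM: fitting, good match | Generic only |
| 4 Positive or negative effects | None | No |
| 5 Interest or intention | AIM: wish to enrol | Yes |
| 6 Relevance to adherence | IAM: applicable, suitable | Generic only |
| 7 Barriers | None | No |
| 8 Ease of implementing | None | No |

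The result is the same on all three forms. None has an open question about the intervention.

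**Step 3: how the count depends on the rule used.**
- Sub-Aim 2.1 forms, generic items accepted: 8 − 5 = 3 uncovered (4, 7, 8).
- Sub-Aim 2.1 forms, explicit wording required: 8 − 3 = 5 uncovered (3, 4, 6, 7, 8).
- Pilot patient forms added, generic items accepted: 2 uncovered (7, 8).
- Pilot patient forms added, explicit wording required: 3 uncovered (3, 7, 8).

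The first line is the relevant one. The pilot forms are completed by exposed patients after Meeting #5, so they cannot supply a Sub-Aim 2.1 result.

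**Step 4: the repeated item.** The delivery and completeness form has 3 delivery items and 6 packaging items, so 9 printed and 8 distinct. The form gives no scoring key, so an equally weighted sum is an assumption.
- Total over the whole form: labelling carries 2/9 = 22.2% as printed and 1/8 = 12.5% without the repeat.
- Total over the packaging block only: 2/6 = 33.3% against 1/5 = 20.0%.
- Example for the whole form, with 0–3 scoring also assumed: a patient at worst on labelling and best on the other seven distinct items scores 7 × 3 = 21. That is 21/27 = 77.8% as printed and 21/24 = 87.5% without the repeat.

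**The case against.** The other side has several fair points.

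**The forms may not be final.** Appendix A, under Design Team Meeting #4, says the acceptability questionnaires are developed during the design process, and all three forms still carry a placeholder for the revised prototype. This stands. It makes the gap easy to close, but the printed forms still lack the items.

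**The team is not without information.** A reader might infer that it redesigns with no data on barriers or ease. The documents do not support that. Aim 1 explores barriers and its findings are presented to the design team. The Appendix C guides and the Sub-Aim 2.2 surveys address ease and difficulty, and Meeting #6 revises the model again. What is missing is the Sub-Aim 2.1 result on the prototype, in time for Meeting #5.

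**Focus groups are still mentioned at this stage.** The consent section refers to an Aim 2.1 focus group, and the milestones list focus groups before the pilot. However, the current Methods specify a survey, Appendix C has no guide for a Sub-Aim 2.1 prototype discussion, and focus groups would not give the descriptive statistics promised.

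**Other survey forms touch on effects.** A reader might infer that no survey form at all asks about effects. That goes too far: the pilot patient questionnaire asks whether peer delivery improved health. It comes after exposure and has no item on negative effects, so it does not fill this gap.

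**The forms match the main protocol.** Table 3 lists satisfaction and interest under acceptability, relevance and fit under appropriateness, and ease under feasibility. This stands, and it supports shortening the Appendix A list as a legitimate repair. Each form's preamble also sets the ratings in the context of taking medication, which gives the generic items some bearing on outcome 6.

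**The total may not be used.** No analysis text refers to it, and Appendix A defines completeness as the fidelity metrics plus packaging checks by the research assistant. This also stands.

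**Conclusion.** The list and the instruments do not match. Three of eight Sub-Aim 2.1 outcomes (4, 7 and 8) have no item on any of the three printed forms, and two more (3 and 6) rest on generic wording. If the plan is followed as printed, those three results cannot be given to Meeting #5. This rests on reading the Appendix B forms as the structured questionnaire named in the Methods.

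The introduction's four domains (cost, complexity, usability, value) are not added to the count. A reader might infer that none is asked about, but the item on meeting needs can reasonably be read as bearing on value, so a count of zero would be a judgement.

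The repeated labelling item is minor. A reader might infer that the completeness outcome is mis-weighted. The documents do not show this, because there is no scoring key, no stated use of the total, and a broader definition of completeness. The 2/9 and 2/6 figures hold only under an equal-weight sum. The repeat should also be checked against the original form: its two separate response lists make a text-conversion fault unlikely but do not exclude one.

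Neither part touches pill-count adherence, fidelity or systolic blood pressure.

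**What to change.** Choose one of two repairs before the Sub-Aim 2.1 forms are finalised.

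1. **Add items.** On all three forms, add one closed item on ease of implementing, one closed item on expected benefit or harm, and one open question on barriers. That is 3 × 39 = 117 further answers in total. The cost is a slightly longer survey and brief coding of one open question.
2. **Shorten the list.** Strike outcomes 4, 7 and 8 from Appendix A, Subaim 2.1, and assign them to Sub-Aim 2.2, consistent with Table 3's placing of ease under feasibility. This adds no respondent burden, but Meeting #5 then works without these results and they reach the team only at Meeting #6.

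For the delivery and completeness form, remove the second labelling item, or replace it with the intended item if the repeat is a slip. If forms have already been completed, count it once at scoring. State how the total is scored and which items it covers. The cost is one line on the form and one sentence of scoring text.

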#### **Design Team Meeting #5: Iteration 1**

##### **Session A:**

- DT members will engage in icebreaker activities and review the last meeting discussions
- The PT4A research team will present and discuss findings from acceptability and appropriateness testing
- DT will group issues raised from the interview surveys into themes and propose intervention updates

##### **Session B:**

- DT will create an updated intervention model and submit this to the study investigators, research team, and Informatics team
- DT will be divided into two groups and participate in FGDs to evaluate their experience during the HCD process

#### **Subaim 2.2: Conduct a pilot of the intervention and evaluate feasibility**

##### **Participants:**

Three health facilities will participate in the pilot (one from each county involved in the study). One peer delivery agent will be hired per facility and will be in close contact with clinicians, pharmacy staff, and patients at each health facility. The study will include all who are involved in the care for these patients and we target to enroll a total of **up to 100 patients** in this phase. **Ten patients per facility.**

##### **Inclusion criteria**

- Greater than 18 years of age.
- Currently enrolled in an AMPATH CDM Program

##### **Exclusion criteria**

- Acute illness requiring immediate medical attention
- Terminal illness
- Inability to provide informed consent

##### **Methods:**

The pilot study will be conducted over a 3-month period. Peers will be paid through the PT4A funds. After recruitment and hiring, they will be on-boarded through a week-long training that will cover: i) basic training on hypertension care, ii) use of the PT4A HIT tool to ensure proper documentation of medication pick-up, medication delivery, and peer-patient encounter documentation; iii) providing psychosocial support for hypertensive patients aimed at supporting medication adherence and promoting patient activation. Peers will use the AMRS system (peers will have access to a tablet with access to the HIT/AMRS system, and technological support will be provided by research and the Ampath informatics team) to request a prescription for a patient in the provider catchment. The AMRS system will send the prescription from the healthcare provider to the pharmacy that covers that network. The pharmacy will prepare individually sealed blister bags in individual single seal bags to lower pilferage. Once packaging is complete, the AMRS system will send a message to the peer with the name, date/time of delivery, location, type of drug, and quantity to ensure the right medication is picked up at the right time. The peer will pick up the prescription and then deliver the medication to the patient, confirming receipt by getting a signature from the patient on the HIT tool. The peer will then request the next installment of medications through the AMRS system, taking into account any pills not consumed (remaining in the blister pack). This cycle will repeat until the patient has to see the clinician again, where the clinician will provide a new prescription. During these deliveries, peers will leverage adherence data to support patients and address any barriers to medication adherence. The overall goal of this psychosocial support will be increasing patient activation.

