Endpoints*:	The primary adherence outcome is the pill count adherence ratio, which is the proportion of prescribed doses taken over a 1-month time period, assessed at the end of the pilot. The primary implementation outcome is fidelity, measured as quantity and quality of intervention delivery as intended, comprised of three components: confirmed medication delivery documented by patient e-signature, peer completion of the HIT form, and quality of data entry into the HIT form.

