## **Sub Aim 2.2: Conduct A Pilot of the Intervention and Evaluate Feasibility.**

We will also conduct a pilot of the strategy for up to **1-year** and conduct further FGDs to evaluate feasibility. We will select three pilot health facilities, one from each county. We will hire one peer delivery agent per facility, train them in core roles and responsibilities, and equip them with

tablets. Each peer will be stationed at a specific health facility and will be able to communicate directly with the clinicians, pharmacy staff, and patients. To maintain patient confidentiality, all research

Table 3: Acceptability, Appropriateness, and Feasibility of the PT4A Intervention	
	Outcomes
Acceptability	

• Satisfaction with the proposed intervention design

• Expressed interest or intention to participate

Appropriateness	

• Perceived relevance of intervention to address adherence

• Perceived fit within existing community and clinical infrastructure

Feasibility	

• Anticipated success of implementing intervention in this setting

• Perceived ease of implementing the intervention

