We will evaluate the impact of the pilot on absolute mean change in SBP and medication adherence from baseline to **up to 1 year**. The primary adherence outcome is the pill count adherence ratio, which is the proportion of prescribed doses taken over a 1-month time period, assessed at the end of the pilot. The primary implementation outcome is fidelity, measured as quantity and quality of intervention delivery as intended, comprised of three components: confirmed medication delivery documented by patient e-signature, peer completion of the HIT form, and quality of data entry into the HIT form.

We will also create a retrospective comparator group of CDM patients, by querying AMRS, matched by sex, age, location and by initial blood pressure level. We will use their recorded blood pressure over time and compare the 3, month, 6 month and 1 year change in blood pressure to those of the patients receiving the PT4A intervention to evaluate the magnitude and variance of the intervention effects.

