For Aim 2, the clinician will invite AMPATH CDM Program patients with uncontrolled hypertension and who are eligible for the study from the health facility to enroll in the study on the day of their routine clinic visit. On that day, research team members will describe the research study and the study protocol, and ensure the patient meets eligibility criteria. For patients randomized to the PT4A intervention arm, participants will be informed the Health Information Technology (HIT) functionality and the availability of peer delivery agents who can deliver the medications to them. As above, extreme care will be taken to fully explain the benefits and risks of the research study, before consent is obtained. Written informed consent will be obtained from all participants. For Aim 2, activities requiring a consent form are the human-centered design FGD and the human-centered design survey. For Aim 2.1, a consent form will be developed and implemented to obtain written informed consent to participate in the FGD. Finally, for Aim 2.2, consent forms will be developed and implemented to obtain written informed consent in the Aim 2.2 FGD and participation in the pilot study. The consent forms will be written in lay terminology at approximately 6th grade level. For FGDs, written informed consent will be obtained in the same manner as above.

Individuals will be free to refuse to participate in the study at any time during the period of the study. A refusal will not impact the health care available to the individual in any manner. Access to care will not be impacted in any manner by an individual's decision to opt out of this research project.

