#### Outcomes and Analysis:

We will collect data on implementation such as completeness of the peer delivery, satisfaction of the patients, patient activation, and fidelity of delivery strategy. Patient satisfaction will be measured through a survey adapted from the AIDS Clinical Research Trials Group tool used extensively throughout Kenya and in the Harambee study. Patient activation will be measured through the Patient Activation Measure assessment developed by Insignia Health. Fidelity will be measured as quantity and quality of intervention delivery as intended, comprised of three components: confirmed medication delivery documented by patient e-signature, peer completion of the HIT form, and quality of data entry into the HIT form, which will be assessed by checking for completeness, accuracy and coherent filling of the responses. Completeness of delivery will include these metrics of fidelity in addition to other quality assurance measures centering on medication packaging as well which will be done by the research assistant as the study goes on. We will also conduct surveys with patients, clinicians, and peer delivery agents, focusing on contextual issues impacting implementation, suggestions for modifications, and concepts of feasibility, that is, if the process of delivery and counseling has been successful or not successful in all the settings and the perceived ease of implementing the intervention. We will also evaluate the impact of the pilot on absolute mean change in SBP and medication adherence. The primary adherence outcome is the pill count adherence ratio, which is the proportion of prescribed doses taken over a 1-month time period, assessed at the end of the pilot.

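### The pilot is 3 months long in Appendix A and up to 1 year in the body, so the 6-month and 1-year blood pressure comparisons and the timing of the primary pill count are not settled

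*Combined protocol and SAP*

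**What the plan says.** Two parts of the combined protocol and SAP give the length of the Sub-Aim 2.2 pilot.

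- Appendix A, Subaim 2.2, Methods: "The pilot study will be conducted over a 3-month period".
- Body, Sub Aim 2.2: "We will also conduct a pilot of the strategy for up to 1-year and conduct further FGDs to evaluate feasibility".

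The same body section sets the analyses. The before-after analysis is the "absolute mean change in SBP and medication adherence from baseline to up to 1 year". For the retrospective comparator group drawn from AMRS, the plan is to "compare the 3, month, 6 month and 1 year change in blood pressure to those of the patients receiving the PT4A intervention". Appendix A (Outcomes and Analysis under Subaim 2.2) gives the before-after analysis no time point: "We will also evaluate the impact of the pilot on absolute mean change in SBP and medication adherence".

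For adherence, the main outcome is a ratio based on pill counts. The synopsis defines it as "the proportion of prescribed doses taken over a 1-month time period, assessed at the end of the pilot". The body and Appendix A use the same definition, and none of the three places names a month.

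The synopsis gives both study duration and participant duration as up to 1 year. Table 4 (Milestones) gives target completion months: Aim 1 coding and analysis M6, the human-centered design process M8, pilot implementation M11, pilot data analysis M12.

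**The concern.** A 3-month pilot fits literally within a ceiling of 1 year, so the two lengths alone are not the whole difficulty. The difficulty is that the body names fixed comparison times of 6 months and 1 year. A 3-month pilot ends before either of them, and the protocol describes no follow-up after the pilot.

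Two things depend on the answer. First, the synopsis says that the comparator is there to help understand the magnitude and variance of the intervention effects. A reading taken months after peer delivery has stopped answers a different question from one taken during delivery. Second, adherence after about 3 months of peer delivery and adherence after a year of it are different quantities, and the text permits either as the primary adherence outcome. Sites could stop at 3 months or continue to 12 and both be following the protocol, and an analyst could settle the assessment month after seeing data.

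**Working it through.** The plan states no sample-size or power figure for the pilot, so there is none to reproduce. The check compares durations.

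**Step 1. Comparison times against a 3-month pilot.** Inputs: length 3 months (Appendix A); comparison times 3, 6 and 12 months (body, Sub Aim 2.2). Time after the pilot ends = comparison time − pilot length.

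- 3 months: 3 − 3 = 0, so the reading falls at the end of the pilot.
- 6 months: 6 − 3 = 3 months after.
- 12 months: 12 − 3 = 9 months after.

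So 2 of the 3 comparisons lie beyond the pilot. With a full 12-month pilot all 3 lie within it.

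**Step 2. Comparison times against the milestone targets, if the body governs.** Aim 2 is to follow completion of Aim 1 activities. In Appendix A the pilot comes after design meetings 1 to 4, the acceptability survey and meeting 5. The M8 design milestone covers brainstorming, conceptualization and creation, which are steps before the pilot. Months available, counting both end months:

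- After Aim 1 coding (M6), to completed pilot analysis (M12): M7 to M12 = 6 months for all remaining work, including design, pilot and analysis. This is below 12.
- After the design work (M8), to pilot implementation (M11): M9 to M11 = 3 months. This is below 6.
- After the design work (M8), to completed pilot analysis (M12): M9 to M12 = 4 months, even with no time set aside for analysis. This is below 6.

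The targets therefore cannot hold 1-year follow-up. Once the design work is done, they cannot hold 6 months either. Deleting the 3-month sentence from Appendix A would not by itself make the plan consistent.

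**Step 3. Timing of the primary pill count.** The window is 1 month long and closes at the end of the pilot.

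- Length 3 months: the window is the third month of the pilot.
- Length 12 months: the window is the twelfth month.
- Difference between these two cases: 12 − 3 = 9 months.

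This is pilot time. The text does not say whether the end of the pilot is one calendar date or each patient's own last day, so it does not fix time since enrolment. Because up to 1 year is a ceiling with no floor, choosing the body's length would still leave the month open.

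**The case against.** The strongest reply is that the 3-month sentence is one unrevised line. The synopsis and the body agree on up to 1 year, and Appendix A has a similar mismatch where it gives up to 100 patients beside ten per facility. That may be so, but the documents do not say it. Appendix A is listed in the contents and carries the same version label as the body. Correcting the line would also leave the milestone conflict and the undated pill count in place.

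Several further objections stand and limit the point.

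- A reader might infer that the 6-month and 1-year comparisons are impossible. The documents do not support that. Pilot patients are in the chronic disease program and their clinical data go into AMRS, so later readings may exist. The reference to patients receiving the intervention can also be read as naming the group. What is lost is the interpretation as continued exposure, and only if the appendix governs.
- A reader might take Table 4 to set the pilot at 2 or 3 months. It does not. Its months are target completion dates, the pilot implementation metric counts patients recruited and reached, and no start month is legible in the extracted text, which is not held against the plan. The table supports only the upper bounds in Step 2.
- A reader might argue that late enrolees would have too little exposure. No enrolment period is stated. The consent section's account of enrolment at clinic visits also mentions randomised patients, so it may not describe this pilot. No exposure figure is derived here. Nor does reaching 3 months depend only on how time is counted; it depends on how long each patient receives delivery.

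The pilot is also formative, with no stated power or confirmatory test. That lowers the severity but does not remove the inconsistency.

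**Conclusion.** The inconsistency is real and should be fixed. Current text gives two pilot lengths without saying which governs.

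- If the 3-month length governs, two of the three planned blood pressure comparisons would rest on routine records made after the pilot and would not measure continued exposure.
- If the longer length governs, the milestone targets do not accommodate 1-year follow-up or, after the design work, 6-month follow-up. This part rests on target dates and on the order of the aims.
- Under either length, the primary adherence outcome has no stated assessment time. The two printed lengths, taken at their full extent, put it 9 months apart.

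The first and third conclusions need no assumption beyond the text. None of this shows which length the sponsor intends, and this review takes no position on that.

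**What to change.** - Reconcile the pilot length in the body (Sub Aim 2.2), in Appendix A (Subaim 2.2, Methods) and in the pilot rows of Table 4, so that one length and one calendar apply throughout.
- State one delivery period per patient.
- Assess the pill-count ratio and the before-after SBP change at one stated time since each patient's enrolment, within that delivery period. Put that time in the synopsis, the body and Appendix A in place of the wording "assessed at the end of the pilot".
- Read the comparator patients at the same time since a stated index visit.
- Keep the 6-month and 1-year comparisons only if the reconciled calendar supports them. Otherwise delete them or label them as post-intervention.

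The cost is protocol wording and a corrected milestone table. Leftover pills are already accounted for at each delivery cycle, so fixing the pill-count time should need no new procedure. The downside is that the later time points may be lost, or the M12 analysis date may have to move.
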